9.8 Study Drug Interruption and Stopping Rules

9.8.1 Liver Function Tests

Parts A

The central laboratory will notify the medical monitor of ALT or AST >3 × ULN and total bilirubin >2 × ULN that are derived from centrally submitted samples.

Subjects with new treatment-emergent ALT or AST elevations of $>3 \times ULN$, with or without total bilirubin $>2 \times ULN$, must be followed closely, including confirmatory testing performed by the central laboratory within 48 to 72 hours of the initial finding and subsequent close monitoring of ALT, AST, and bilirubin levels, as clinically indicated.

If a subject cannot return to the site for confirmatory testing, a local laboratory may be used. Local laboratory results must be reported immediately to the medical monitor, and the subject must have the tests repeated and sent to the central laboratory as soon as possible (ideally within 48 to 72 hours).

Study drug administration must be interrupted immediately (prior to confirmatory testing) if any of the following criteria are met:

- ALT or AST >8 × ULN
- ALT or AST >5 × ULN for more than 2 weeks
- ALT or AST >3 × ULN, in association with total bilirubin >2 × ULN and/or clinical jaundice

A thorough investigation of potential causes should be conducted, and the subject should be followed closely for clinical progression.

Study drug administration **must be discontinued** if the following criteria are met:

• Subsequent ALT or AST values confirm the initial elevation that satisfied the interruption rule (above), and no convincing alternative etiology (e.g., acetaminophen use, viral hepatitis, alcohol ingestion) is identified, regardless of whether transaminase levels have improved

All subjects in whom treatment is discontinued for elevated transaminases (and bilirubin, as applicable) should have these levels monitored closely until levels normalize or return to baseline.

If an alternative, reversible cause of transaminase elevation with or without increased bilirubin or clinical jaundice has been identified, study drug administration may be resumed once transaminases return to baseline or are ≤2 × ULN, whichever is higher. Regardless of the duration of interruption, the medical monitor should be notified prior to resumption of study drug. Upon resumption of study drug, transaminases and bilirubin should be assessed weekly for 4 weeks. If a protocol-defined transaminase elevation interruption threshold recurs within 4 weeks of rechallenge with the study drug (with confirmation of the initial elevation by repeat testing within 48 to 72 hours), then the study drug must be permanently discontinued, regardless of the presumed etiology.

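### After a liver interruption involving raised bilirubin or jaundice, the restart rule in protocol section 9.8.1 sets a transaminase level but no bilirubin or jaundice condition

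*Protocol*

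**What the plan says.** Section 9.8.1 of the protocol requires immediate interruption for ALT or AST above 8 × ULN, for ALT or AST above 5 × ULN lasting more than 2 weeks, or for "ALT or AST >3 × ULN, in association with total bilirubin >2 × ULN and/or clinical jaundice".

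Two routes lead on from there.

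- **Discontinuation.** If later ALT or AST values confirm the elevation and "no convincing alternative etiology (e.g., acetaminophen use, viral hepatitis, alcohol ingestion) is identified, regardless of whether transaminase levels have improved", study drug must be stopped for good. For those whose treatment is discontinued, the section says that subjects with "elevated transaminases (and bilirubin, as applicable) should have these levels monitored closely until levels normalize or return to baseline".
- **Restart.** If "an alternative, reversible cause of transaminase elevation with or without increased bilirubin or clinical jaundice has been identified", then "study drug administration may be resumed once transaminases return to baseline or are ≤2 × ULN, whichever is higher". The section adds: "Regardless of the duration of interruption, the medical monitor should be notified prior to resumption of study drug". After restart, transaminases and bilirubin are checked weekly for 4 weeks. Study drug is stopped permanently if a transaminase interruption threshold is met again in that time and confirmed on repeat testing.

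**The concern.** One of the three interruption triggers has two parts: a transaminase part and a bilirubin or jaundice part. The restart rule names both parts when it describes the cases it covers, but it sets a recovery level for only the first. A child interrupted for the combined finding therefore meets the written restart level once transaminases have fallen, whatever the bilirubin and whether or not the child is still jaundiced.

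What is at stake is re-exposure of a child whose liver event has only partly resolved. It is a matter of subject safety and not of estimation. A site acts on this dosing rule directly, so it is not a detail that would normally be left to a statistical analysis plan.

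**Working it through.** No figure in the protocol depends on this rule, so there is nothing to reproduce. The check compares the texts and then works out how much of Part A the rule can reach.

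**1. Triggers against restart conditions (section 9.8.1)**

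| Step | Transaminase element | Bilirubin or jaundice element |
|---|---|---|
| Trigger 1 | above 8 × ULN | none |
| Trigger 2 | above 5 × ULN for more than 2 weeks | none |
| Trigger 3 | above 3 × ULN | total bilirubin above 2 × ULN and/or jaundice |
| Restart: cause | alternative, reversible cause identified | named as within scope, no level set |
| Restart: level | baseline or ≤2 × ULN, whichever is higher | none |
| Restart: medical monitor | notified beforehand | none |

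One of 3 triggers has a bilirubin or jaundice element. None of the 3 restart conditions sets a level for it.

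**2. Is the omission explained by scope?** No. The restart rule covers cases with or without raised bilirubin or jaundice, so the combined finding is inside it.

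**3. Is the condition set elsewhere?** The other places that could supply it do not.

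- Section 8.2 excludes a child with total bilirubin ≥2 × ULN, but only at screening.
- The text on bilirubin normalizing in 9.8.1 is a monitoring instruction for subjects whose treatment is discontinued.
- Close monitoring of bilirubin after a new ALT or AST elevation is as clinically indicated, with no level attached.
- Sections 9.7 (withdrawal for unacceptable toxicity) and 9.9 (withdrawal at the discretion of the investigator or sponsor) name no bilirubin level.
- The weekly bilirubin checks begin only after dosing has resumed. The recurrence rule is tied to a transaminase threshold, so a bilirubin result alone does not activate it.

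**4. What the rule permits.** Take a child interrupted under trigger 3, with a reversible cause identified, transaminases down to ≤2 × ULN and the medical monitor notified. Every written condition is met. Total bilirubin may still be above 2 × ULN, a level that would have barred the child from entry under section 8.2.

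**5. Reach in Part A.**

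- Sample size: about 12 children (section 12.1).
- Scheduled serum chemistry during dosing: Days 1, 8 (± 1) and 15 (± 1) (Table 3-2). The Day 1 sample is taken before the first dose.
- Last dose: the morning of Day 15 (section 9.6.1).
- The Day 15 sample is too late to lead to an interruption and restart, so only the Day 8 draw is a scheduled opening.
- Nominal time left after it: 15 − 8 = 7 days, less laboratory turnaround.

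Within that time four things must all happen: transaminases fall to the restart level, a reversible cause is found, bilirubin or jaundice lags behind, and the investigator chooses to restart. An unscheduled test or visible jaundice could open the path earlier. The documents give no rate for any of these steps, so I put no probability on the sequence.

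**The case against.** The strongest defence is that the rule leaves bilirubin to clinical judgement on purpose, and that judgement is well supported.

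- The central laboratory alerts the medical monitor: "The central laboratory will notify the medical monitor of ALT or AST >3 × ULN and total bilirubin >2 × ULN". After an interruption, "A thorough investigation of potential causes should be conducted, and the subject should be followed closely for clinical progression".
- Restart is allowed, never required.
- The condition that a reversible cause be found can reasonably be read as requiring that the whole picture, jaundice included, be explained.
- The section is driven by transaminases throughout. Raised bilirubin alone is never a trigger, and once ALT and AST are at or below 2 × ULN the combined trigger is no longer met.
- The contrast with discontinued subjects is weak, because that sentence concerns monitoring and does not show an intended restart threshold.

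Much of this stands. Bilirubin is not ignored; what is missing is a recovery condition. But the protocol did not leave restart to judgement alone. It wrote a numeric level, and that level covers only one part of the trigger. Finding a cause does not show that the event has resolved. The medical monitor is told of the restart and is not asked to approve it.

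A reader might draw three stronger conclusions that the text does not support.

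- **That the section contradicts itself.** It does not; a condition is absent from a stated rule.
- **That children with unexplained liver injury may be rechallenged.** A confirmed elevation with no convincing alternative cause requires discontinuation, even if transaminases have improved.
- **That the gap matters more in a second, longer part.** The 4-week recheck period in 9.8.1 and the Week 20 liver tests in section 11.5.2 suggest that the text was also written for one. The visible document does not describe such a part, so reach there cannot be judged.

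**Conclusion.** The point holds as an omitted safety condition of the lowest severity. For a child with an identified reversible cause, section 9.8.1 permits re-dosing while total bilirubin is above 2 × ULN or jaundice persists.

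In Part A, few if any of about 12 children would come to this path, since only the Day 8 draw is scheduled early enough to open it. No PK parameter, estimate or analysis changes. The conclusion rests on reading the restart conditions as the complete written list. A site that read the reversible-cause requirement as also demanding recovery of bilirubin would already behave safely, but the text does not oblige it to.

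**What to change.** Amend only the restart sentence in 9.8.1. After the transaminase level, add: *and, if total bilirubin was >2 × ULN or clinical jaundice was present at or at any time during the interruption, total bilirubin is <2 × ULN (or a stricter level set by the sponsor's clinicians) and clinical jaundice has resolved.*

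- **Coverage.** The wording also catches a child interrupted for transaminases alone whose bilirubin then rises.
- **Level.** Below 2 × ULN matches the entry limit in section 8.2 and sits under the interruption trigger. A return-to-baseline alternative, as used for transaminases, is hardly needed, because eligibility already requires a screening value below 2 × ULN.
- **Left alone.** The discontinuation and recurrence sentences stay as they are. A never-interrupted child with isolated raised bilirubin is handled as now. That difference is deliberate, because the interrupted child has just had a liver event.
- **Cost.** One clause. Total and direct bilirubin are already in the serum chemistry panel (Table 11-2), alongside the transaminases that must be rechecked before restart, so no new type of test is needed. The downside is an occasional delayed or forgone restart, which within a 15-day dosing period may mean that a child does not resume.

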9.8.2 Rash

Parts A

Individuals who develop a generalized rash will be monitored closely. Study drug dosing should be interrupted if a subject develops a generalized rash of Grade 3 or higher, or a rash that is considered a serious adverse event (SAE). The investigator will notify the medical monitor of any rash that results in interruption of study drug, is Grade 3 or higher (Section 13.1.1.4), or is an SAE. Investigators should consider additional evaluation including laboratory testing (e.g., complete blood count with differential, liver function tests), photographs of the rash, and dermatology consultation. The investigator may consider resumption of study drug if considered clinically appropriate.

9.9 Removal of Subjects

Parts A

Subjects may withdraw from the study at any time at their own request. Subjects may be withdrawn from study drug treatment at any time at the discretion of the investigator or Vertex for safety, behavior, noncompliance with study procedures, or administrative reasons. If a subject has been withdrawn from study drug treatment, the subject will continue to be followed, provided that the subject has not withdrawn consent (and assent, as applicable).

In addition, a subject must be discontinued from study drug treatment if the subject meets any of the following criteria:

- Has a screening CFTR genotype that does not confirm study eligibility if a previous CFTR genotype laboratory report was used to establish eligibility. These subjects must be discontinued from the study (Section 8.1)
- Meets any of the stopping (discontinuation) criteria (Section 9.8)
- Has a QTcF value above the threshold for repeat measurement (Section 11.5.4)
- Becomes pregnant (Section 11.5.6.2)

Subjects who discontinue study drug treatment should return for study assessments, as noted in Section 9.1.4.

If a subject does not return for a scheduled visit, reasonable effort will be made to contact the subject. In any circumstance, reasonable effort will be made to document subject outcome. The investigator will inquire about the reason for withdrawal, request that the subject return all unused investigational product(s), request that the subject return for an ETT Visit and Safety

Follow-up Visit, if applicable (see Section 9.1.4), and follow up with the subject regarding any unresolved AEs.

If the subject withdraws consent or assent for the study, no further assessments will be performed. Vertex may retain and continue using the study data and samples after the study is over, and may use the samples and information in the development of the study compound, and for other drugs and diagnostics, in publications and presentations, and for education purposes. If the subject withdraws from the study, the study data and samples collected will remain part of the study. A subject will not be able to request the withdrawal of his/her information from the study data. A subject may request destruction of the samples collected from him/her during the study as long as those samples can be identified as his/her samples.

9.10 Replacement of Subjects

Part A Only

Subjects who withdraw or are withdrawn for nonsafety reasons during the Treatment Period may be replaced as needed in Part A,

10 STUDY DRUG INFORMATION AND MANAGEMENT

Parts A

Study drug refers to VX-659/TEZ/IVA.

10.1 Preparation and Dispensing

Parts A

Study drug may be dispensed only under the supervision of the investigator or an authorized designee and only for administration to the study subjects.

10.2 Packaging and Labeling

Parts A

Study drug tablets will be supplied in blister cards by Vertex. Study drug labeling will be in compliance with applicable local and national regulations. Additional details regarding packaging, labeling, and dispensing for study drug will be in the Pharmacy Manual.

10.3 Study Drug Supply, Storage, and Handling

Parts A

Table 10-1 provides the study drug information. The investigator, or an authorized designee (e.g., a licensed pharmacist), will ensure that all investigational product is stored in a secured area, under recommended storage conditions, and in accordance with applicable regulatory requirements. Detailed instructions regarding the storage, handling, and dispensation of the study drug will be provided in the Pharmacy Manual.

Table 10-1 Study Drug: Strength/Dosing Form/Route

Drug Name, Dosing Form, Route	Strength		
	Part A: All Subjects		
VX-659/TEZ/IVA, FDC tablet, oral			
VX-659	120 mg		
TEZ	50 mg		
IVA	75 mg		
IVA, tablet, oral	75 mg		

FDC: fixed-dose combination; IVA: ivacaftor; TEZ: tezacaftor

10.4 Drug Accountability

Parts A

The pharmacist or designated study site staff will maintain information regarding the dates and amounts of (1) study drug received; (2) study drug dispensed to the subjects; and (3) study drug returned by the subjects. Subjects will be instructed to return all used and unused materials associated with the study drug to the site. These materials will be retained at the site according to instructions provided by Vertex or its designee. The study monitor will review study drug records and inventory throughout the study.

If a site uses a site-specific drug accountability system and/or process, including processes associated with the destruction of returned materials, the process must be documented and approved by Vertex. The study monitor must review the drug accountability documentation on a regular basis. The study monitor will promptly communicate to Vertex any discrepancies he/she is unable to resolve with the site.

10.5 Disposal, Return, or Retention of Unused Drug

Parts A

The study site staff or pharmacy personnel will retain all materials returned by the subjects until the study monitor has performed drug accountability. The investigator will ensure that the materials are destroyed in compliance with applicable environmental regulations, institutional policy, and any special instructions provided by Vertex. Destruction will be adequately documented.

10.6 Compliance

Parts A

To ensure treatment compliance, the investigator or designee will supervise all study drug dosing that occurs at the site. At each visit, site personnel will review that the subject is compliant with study drug dosing and remind the subject of study drug dosing requirements. Compliance will also be assessed by ongoing study drug count.

If a subject demonstrates continued noncompliance of study drug dosing despite educational efforts, the investigator should consider discontinuing the subject from the study.

10.7 Blinding and Unblinding

Parts A

This will be an open-label study; however, subjects and their legally appointed and authorized representative (e.g., parent or legal guardian) should not be informed of their results during the Treatment Period, regardless if the subject permanently discontinues treatment.

[figure not shown]
11 ASSESSMENTS

The timing of assessments is shown in Table 3-1 through Table 3-4.

The following assessments must be performed in the order specified below when more than 1 assessment is required at a particular time point:

Parts A

- 1. Vital signs
- 2. Pulse oximetry
- 3. Standard 12-lead ECG recordings
- 4. Safety laboratory assessments
- 5. PK sampling may be performed in either order when occurring at the same time point. PK blood samples collected before dosing must be collected within 60 minutes before dosing as described in Section 11.2.1.

11.1 Subject and Disease Characteristics

Parts A

Subject and disease characteristics include the following: demographics, medical history, height, and weight.

Medical history will be elicited from each subject and extracted from medical records during screening. Based on the medical history, the subject will be assessed for any disqualifying medical conditions as specified in the inclusion and exclusion criteria. The medical history will include a complete review of systems, medical and surgical histories, and any allergies.

11.2 Pharmacokinetics

11.2.1 Blood Sampling

Parts A

Blood samples will be collected to determine plasma concentrations of VX-659, TEZ, M1-TEZ, IVA, and M1-IVA. These samples may also be used to evaluate metabolites of VX-659 and additional TEZ and IVA metabolites, for further evaluation of the bioanalytical method,

All efforts should be made to obtain the PK samples at the exact nominal time relative to dosing. Acceptable windows for sampling times are shown in Table 11-1. Samples collected outside of these acceptable windows will be considered protocol deviations.

Table 11-1 Acceptable Pharmacokinetic Sampling Windows

Sampling Time	Time From Scheduled Sampling Allowed
predose (before morning dose)	within 60 minutes before dosing
>0.25 and <6 hours after morning dose	± 10 minutes
≥6 hours after morning dose	± 30 minutes

For each visit with a PK blood draw, a record of study drug administration will be collected as described in Section 9.6. The collection date and exact time that each PK blood sample is drawn will also be recorded.

Samples from the PK sampling will be kept frozen by Vertex or its designee until all analyses have been completed and then disposed of according to Vertex or designee standard operating procedures.

11.2.2 Processing and Handling of Pharmacokinetic Samples

[figure not shown]
Parts A

Detailed procedures for the collection of blood samples and further procedures for processing and handling of samples for PK analysis will be provided in the PK Sample Handling Guidelines

11.2.3 Bioanalysis

Parts A

Samples will be analyzed using validated analytical methods in compliance with Vertex or designee standard operating procedures. A description of the assays and validation data will be provided in separate reports.

11.4 Efficacy

[figure not shown]
11.4.1 Spirometry

Parts A

Spirometry will be performed according to the American Thoracic Society Guidelines¹³ and according to the additional guidelines that follow.

Pre-bronchodilator spirometry is defined as spirometry testing performed for subjects who have

- withheld their short-acting bronchodilators (e.g., albuterol) or anticholinergic (e.g., ipratropium bromide [Atrovent[®]]) for more than 4 hours before the spirometry assessment;
- withheld their long-acting bronchodilator (e.g., salmeterol) for more than 12 hours before the spirometry assessment; and
- withheld their once-daily, long-acting bronchodilator (e.g., tiotropium bromide [Spiriva®]) for more than 24 hours before the spirometry assessment.

All sites will be provided with spirometers to be used for all study assessments. Spirometry data will be transmitted to a centralized spirometry service for quality review. The investigator's assessment of the spirometry results will be used for the screening assessment and determination of eligibility.

See Section 10.7 for information about access to spirometry results.

The measured spirometric values listed below will be converted to percent predicted values using the standard equations of GLI.⁶

• FEV₁ (L)

11.4.4 Height and Weight

Parts A

Height and weight will be measured with shoes off and before the dose of the study drug during the Treatment Period.

11.5 Safety

Parts A

Safety evaluations will include reporting of AEs, clinical laboratory assessments, physical examinations (PEs), clinical evaluation of vital signs, pulse oximetry, standard 12-lead ECGs, and ophthalmologic examinations.

Medical history and PE information will be collected during the course of the study and will be captured in the source documentation. Physical examinations post-baseline will not be captured for inclusion into the study database. However, any untoward findings identified on PEs conducted after the administration of the first dose of study drug will be captured as an AE if

those findings meet the definition of an AE. Demographic data collected at the Screening Visit will be included in the study database.

11.5.1 Adverse Events

Parts A

All AEs will be assessed, documented, and reported in accordance with ICH GCP guidelines. Section 13.1.1 outlines the definitions, collection periods, criteria, and procedures for documenting, grading, and reporting AEs. Electronic AE case report form (CRF) completion guidelines for investigators as well as training will be provided.

